5.4 CONCOMITANT THERAPY

5.4.1 Prohibited Therapy

Treatments that the investigator considers necessary for a subject's medical needs may be administered except for the following prohibited therapies. If any of the following therapies is required by a subject as per the investigator's assessment, the subject's eligibility for continuing investigational treatment will be determined at the investigator's discretion in consultation with the sponsor medical monitor.

- 1. Anti-tumor therapies: no other anti-tumor therapy than the investigational product is permitted. This includes but is not limited to chemotherapy, immunotherapy, biologically targeted therapy, and traditional Chinese medicines with anti-tumor indications; and radiation therapy.
- 2. Concurrent investigational agent (unapproved medications) other than CS1001.
- 3. Immunosuppressant (unless for treating AEs).
- 4. Systemic corticosteroids (of dose higher than 10 mg prednisone or equivalent per day), unless for conditions specified in Section 5.4.2 Item 2, or for treating AEs.
- 5. Live vaccines are prohibited during the study.
- 6. Other prohibited treatment as specified in the inclusion/exclusion criteria.

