4.3 Discontinuation and Withdrawal

4.3.1 Discontinuation of Study Treatment

Subjects must discontinue study treatment if any of the following criteria are met:

- 1. Any AE that meets the treatment discontinuation criteria specified in the protocol (refer to Section 5.3).
- 2. Disease progression. (Subject who meets the criteria for treatment beyond progression may continue treatment until confirmation of progressive disease by tumor assessment. Refer to Section 3.1.2.1.)
- 3. Subjects who receive any prohibited treatment during the trial that compromises the assessment of safety and efficacy may be determined to discontinue study treatment by the investigator in consultation with the sponsor medical monitor.
- 4. Any intercurrent condition that compromises the subject's ability to continue study treatment.
- 5. Pregnancy of female subjects.
- 6. Subjects and/or their legal guardian who decide to discontinue the study treatment may inform the subject's doctor at any time and then discontinue study treatment. According to the Deceleration of Helsinki and other applicable regulatory requirements, all subjects have the right to withdraw from the study at any time and for any reason. The doctor and the study site must not hold bias in their future treatment.
- 7. Subject with poor compliance who doesn't receive treatment at the right dose and the right time despite the investigator's effort in communication and coordination, which may lead to significant uncorrectable bias in the study results may be determined to discontinue study treatment by the investigator in consultation with the sponsor medical monitor.
- 8. Other conditions that make study treatment continuation inappropriate judged by the investigator.

In any case, the primary reason for study treatment discontinuation will be recorded in the original medical record. For subjects who discontinue study treatment for any reason, the investigator should try every effort to have the subject complete end of study visit if the subject has received at least one dose of the investigational product, and continue to follow up subjects with unresolved AE.

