8.3 Efficacy Analyses

8.3.1 Primary Efficacy Endpoints

The primary efficacy endpoint, objective response evaluated by IRRC, refers to CR or PR determined by IRRC based upon Lugano 2014 classification. For subjects who fail to meet the above criteria or fail to receive any tumor assessment after baseline will be considered as non-responder.

ORR is the rate of objective responders. The population involved in the IRRC-ORR analysis are EAS subjects with evaluable or measurable lesion at baseline confirmed by IRRC.

The 95% confidence interval (CI) of ORR will be calculated using the exact binomial (Clopper-Pearson) method to evaluate the precision of the ORR estimate.

The statistical analysis will be performed by 24 weeks after the first dose of the last subject.

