The primary efficacy endpoint is ORR by IRRC based upon Lugano 2014 classification, defined as the proportion of subjects who achieve complete response (CR) or partial response (PR) as the best overall response. Subjects who did not have any post-baseline tumor assessment will be considered as non-responders.

The IRRC-ORR analysis will include subjects with evaluable or measurable lesion at baseline as confirmed by IRRC in EAS.

The 95% CI of ORR will be calculated using the exact binomial (Clopper-Pearson) method to evaluate the precision of the ORR estimate.

Secondary Efficacy Endpoints

The ORR assessed by investigators will be analyzed and provided as described in Section 0. Proportions of subjects who achieve CR, PR, stable disease (SD), and progressive disease (PD) per IRRC evaluation and their 95% CIs will be summarized. This analysis will be performed for subjects with evaluable or measurable lesion at baseline as confirmed by IRRC in EAS. Proportions of subjects with responses per investigator's evaluation and their 95% CIs will also be summarized as for IRRC. This analysis will be performed for subjects with evaluable or measurable lesion at baseline as confirmed by investigators in EAS.

Duration of response (DoR) is defined as the time from the first documented CR or PR (whichever comes first) to the first documented disease progression or death, whichever comes first. DoR will be evaluated in subjects with objective responses per investigator's or IRRC's assessment, respectively. Subjects without event (disease progression or death) as of data cutoff will be censored at the date of the last tumor assessment. If no tumor assessment is performed after the first occurrence of CR or PR, DoR will be censored at the date of first CR or PR. Subjects with subsequent anti-cancer therapy(if any) before event will be cencored at the date of last tumor assessment prior to the initiation of therapy. If an event is observed immediately after two or more consecutive missed tumor assessments, subjects will be censored at the date of last tumor assessment prior to the missing tumor assessments. Kaplan-Meier methodology will be used to analyze DoR and the KM curve will be constructed.

Time to response (TTR) is defined as the time from the first study dose to the first documented CR or PR, whichever comes first. TTR will only be evaluated for subjects

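### Best overall response has no cut-off at other anti-tumor therapy given while CS1001 continues, and the SAP's DoR censoring rule does not fit responses first seen after such therapy

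*Protocol*

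**What the plan says.** **Treatment rules.** Item 1 of Protocol 5.4.1 states that "no other anti-tumor therapy than the investigational product is permitted", and its list includes chemotherapy, targeted therapy and radiation. For a subject who needs any prohibited therapy, the same section says that "the subject's eligibility for continuing investigational treatment will be determined at the investigator's discretion in consultation with the sponsor medical monitor". Protocol 4.3.1 item 3 concerns subjects given prohibited treatment that compromises the assessment of safety and efficacy. It stands under a header of mandatory stopping criteria, but its own wording is that such subjects "may be determined to discontinue study treatment by the investigator in consultation with the sponsor medical monitor".

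**Primary endpoint.** The SAP (Primary Efficacy Endpoint) has ORR "defined as the proportion of subjects who achieve complete response (CR) or partial response (PR) as the best overall response". Its only explicit non-responder rule is "Subjects who did not have any post-baseline tumor assessment will be considered as non-responders". Protocol 8.3.1 likewise makes non-responders of subjects who do not meet CR or PR, or who "fail to receive any tumor assessment after baseline will be considered as non-responder". Neither text, nor Protocol 8.8, refers to other anti-tumor therapy.

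**DoR.** The SAP (Secondary Efficacy Endpoints) starts DoR at the first CR or PR and adds: "Subjects with subsequent anti-cancer therapy(if any) before event will be cencored at the date of last tumor assessment prior to the initiation of therapy". SAP Appendix 4 records that two DoR censoring rules were added in response to FDA comments; it lists no matching change for ORR. The protocol's DoR text (8.3.2) has no such rule.

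**Imaging.** Protocol 6.4 and Table 1 note 20 end scheduled tumor assessment when new anti-cancer treatment starts. Table 4, which sets the 12-weekly scans during treatment, does not repeat that stop.

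**The concern.** The DoR rule accepts that once another therapy starts, the course of the disease can no longer be attributed to CS1001 alone. The primary endpoint has no matching limit. In a single-arm trial there is no control group in which a response produced by radiotherapy or chemotherapy would show up. Compared with an analysis that stops at the other therapy, the omission can only raise ORR or leave it unchanged.

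The DoR rule raises a second problem. It ties the censoring date to the start of the therapy and says nothing about the order of therapy and response. If the therapy comes first, the censoring date can fall before DoR begins, and that subject is in the ORR numerator without a valid duration.

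**Working it through.** The plan gives no figure for this point, and the visible text does not show the sample-size basis, so there is no stated number to reproduce. The check has two parts.

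**1. Following the rules for one subject**

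Inputs: scans every 12 weeks from first dose (Protocol 6.4, Table 4); DoR start and censoring rule from the SAP. Baseline is taken as week 0. The subject continues CS1001 by discretion and has a first PR at a scan after the other therapy.

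DoR = (date of last assessment before the therapy) − (date of first CR or PR).

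| Other therapy starts | Last assessment before it | First CR/PR | DoR under the censoring rule |
|---|---|---|---|
| Week 8 | Week 0 | Week 12 | 0 − 12 = −12 weeks |
| Weeks 13 to 23 | Week 12 | Week 24 | 12 − 24 = −12 weeks |
| Weeks 13 to 23 | Week 12 | Week 36 | 12 − 36 = −24 weeks |

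Any response first seen after the therapy gives a negative value if the rule applies. Whether it applies depends on a term that neither document defines:

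- *On-study therapy is not new or subsequent therapy.* Scans continue, the response counts in ORR, and DoR is not censored for the therapy. The response and its whole duration go to CS1001. Table 1 favors this reading, because it schedules collection of subsequent anti-cancer treatment only at the radiology and survival follow-up visits.
- *On-study therapy is new or subsequent therapy.* Protocol 6.4 and Table 1 note 20 end scheduled scans, so a later response is recorded only if scanning goes on. That is possible, because treatment continues and Table 4 carries no stop. The response then counts in ORR and DoR is negative, as tabulated.

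Neither reading gives a satisfactory result once a later response has been recorded.

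**2. What one response is worth (illustration)**

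Inputs: about 80 subjects planned (Protocol 4), assumed all to be in the IRRC-ORR denominator; historical control 20% (Protocol 3.2.3); two-sided 95% Clopper-Pearson interval (Protocol 8.3.1 and SAP). With x responders among n, the limits are the 0.025 quantile of Beta(x, n − x + 1) and the 0.975 quantile of Beta(x + 1, n − x).

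One recoded response changes ORR by 1/n: 1/80 = 1.25 points, 1/75 = 1.33, 1/70 = 1.43.

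| Responders | ORR | 95% CI |
|---|---|---|
| 24/80 | 30.0% | 20.3% to 41.3% |
| 23/80 | 28.8% | 19.2% to 40.0% |
| 32/80 | 40.0% | 29.2% to 51.6% |
| 29/80 | 36.3% | 25.8% to 47.8% |

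At n = 80, 24 is the smallest count whose lower limit exceeds 20%, and recoding one response takes the limit below it. The same happens at 23/75 (lower limit 20.5%) against 22/75 (19.4%), and at 22/70 (20.9%) against 21/70 (19.6%). Away from the boundary, recoding three responses (32/80 to 29/80) leaves the lower limit at 25.8%.

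**The case against.** The strongest objection is that the two defects need opposite readings of the same therapy. For a later scan to be on schedule, on-study radiotherapy must not be new anti-cancer treatment; for DoR to be censored before the response, it must be subsequent anti-cancer therapy. A reader might infer that one subject is bound to be both credited in ORR and censored before responding. The documents do not support that: the two coincide only if the therapy counts as new and scanning continues all the same. What stands is that the term is undefined and that neither reading is handled properly.

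It is also fair that the ORR credit comes from silence, not from a written rule. The SAP describes an independent oncologist who sees available clinical data and sets the final response at each visit under the IRRC charter. The charter is not among the documents and may deal with intervening therapy. It cannot be assumed to, and the SAP does not say which visits feed best overall response. The charter would in any case not evidently govern the investigator-assessed endpoints.

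The protocol has safeguards. The therapy is prohibited, item 3 of 4.3.1 is directed at treatment that compromises assessment, and major deviations are summarized and listed. These may keep such cases few and visible, but they do not determine how a case is analyzed. The one sensitivity analysis listed in the SAP repeats IRRC-ORR in the safety analysis set and does not address it.

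Lastly, a reader might infer from 24/80 against 23/80 that a single such response would decide the trial. The visible text gives no success rule against 20%; the interval is said to describe precision. The comparison is an illustration at a chosen boundary.

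**Conclusion.** The concern holds in this form. CS1001 may continue by discretion after prohibited anti-tumor therapy, best overall response is not limited to assessments before that therapy, and the DoR censoring rule does not require the therapy to follow the response. Depending on the undefined term, a response first seen after other therapy may enter the primary ORR either with its full duration or, if scanning continues, with a censoring date before the response. The imaging stop in Protocol 6.4 and Table 1 note 20 reduces the exposure but does not remove it.

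The size is 1.25 ORR points for each affected subject if 80 are analyzed. The documents do not indicate how many subjects would be affected, and it could be none. The effect on interpretation is small unless the result lies close to 20%. The conclusion assumes that the IRRC charter contains no cut-off of its own. The SAP should be amended, because the gap concerns the primary endpoint and costs little to close before database lock.

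**What to change.** In the SAP:

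1. Define other anti-cancer therapy once, to include any therapy under Protocol 5.4.1 item 1 and radiotherapy given while CS1001 continues.
2. Derive IRRC and investigator ORR, CRR, PRR and TTR only from tumor assessments up to the start of that therapy. A subject whose first CR or PR is seen later is a non-responder and stays in the denominator.
3. Use the same definition in the DoR rule, and apply the censoring only to therapy started after the first response. The response assessment itself then precedes the therapy, so the censoring date cannot be earlier than the DoR start. ORR and DoR will also refer to the same responders.

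The sponsor should check that the IRRC charter agrees with this. It should also confirm that dates of on-treatment therapy, radiotherapy in particular, are captured: Table 1 records concomitant medications at treatment visits but schedules subsequent anti-cancer treatment only in follow-up. Protocol 4.3.1, 5.4.1, 6.4 and Table 4 need to be reconciled by the sponsor on treatment and scanning after a prohibited therapy; no clinical rule is proposed here.

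The cost is a few sentences in the SAP and possibly a data-capture check. The downside is that ORR may fall slightly.

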5.4.2 Permitted Therapy

- 1. Inactivated or attenuated influenza vaccine that doesn't require wash-out. The use of other inactivated or attenuated preventive vaccines will be determined according to the actual condition after discussion with the investigator and sponsor's medical monitor.
- 2. Topical, ophthalmic, intra-articular, and nasal and inhaled corticosteroids (with very little systemic absorption) are permitted. Adrenal replacement with $\leq 10 \text{ mg}$ corticosteroid per day or equivalent is permitted. Short-course (<3 weeks) of corticosteroid as prophylaxis (for contrast allergy) or treatment for non-autoimmune diseases (for example delayed-type hypersensitivity caused by allergen contact).

- 3. Symptomatic and supportive treatment for AEs during the study treatment is permitted.
- 4. Other permitted treatment as specified in the inclusion/exclusion criteria.

6. STUDY PROCEDURES AND ASSESSMENTS

Study procedures and assessments should be performed at the planned time points (refer to Table 1). Refer to Section 6.1 for details.

Once a subject is included in this trial, the subject must be informed of the study's nature and procedures, and a signed, written informed consent must be obtained before any study-related procedure.

6.1 STUDY PROCEDURES

6.1.1 Screening

The screening period is from D-28 to D-1. The assessments to be completed during screening are listed in Table 3:

Items	Note		
Study Management Procedures			
Inclusion/exclusion criteria	Assess the subject's eligibility according to the inclusion/exclusion criteria		
Demographics and medical history	 Age, sex, ethnicity, smoking and alcohol use history Pathohistology, clinical stage, tumor-related symptoms 		
Prior medications and concomitant medications	 Treatment regimens with administration methods, starting time and ending time, best response and cause for discontinuation for prior local or systemic anti-cancer therapies Concomitant medications within 28 days before the first investigational product dosing 		
(Clinical Procedures and Assessments		
Adverse events	AEs that occur after obtaining informed consent and before the administration of the investigational product		
Electrocardiogram (ECG)	Standard 12-lead ECG will be used		
Height, weight, and vital signs	The vital signs include temperature, blood pressure, pulse, and respiratory rate		
Physical examination and ECOG performance status	Conduct Physical examinationScore ECOG PS		
Labo	oratory Procedures/Assessments (at site)		
Pregnancy test	Blood human chorionic gonadotrophin test is performed as a pregnancy test within 7 days before the first dose of study treatment		
Hematology, serum chemistry, urinalysis	 Hematology, serum chemistry, and urinalysis tests are performed within 7 days before the first dose Hematology: complete blood count (CBC) and hemoglobin Serum chemistry: blood urea/urea nitrogen, creatinine, sodium, 		

Table 3 Visit procedures in the screening phase

Items	Note	
	potassium, magnesium, chloride, calcium, phosphate, fasting glucose, total bilirubin, direct bilirubin, ALT, AST, alkaline phosphatase, lactate dehydrogenase, total cholesterol, total protein, and albumin	
	• Urinalysis: specific gravity, pH, glucose, protein, cast, ketones, and blood cells	
Coagulation	PT, APTT, and INR	
	All subjects must receive anti-HIV antibody, HBsAg, and anti-HCV antibody tests	
Virology	 Subjects with positive HBsAg must further undergo HBV DNA test 	
	• Subjects with positive anti-HCV antibody must further undergo HCV RNA test	
Thyroid function	Thyroid function tests including FT3, FT4, and TSH will be performed within 7 days before the first dose of study treatment	
EBV DNA	Blood sample collection	
Laboratory	Procedures/Assessments (by central laboratory)	
Central pathology	Stained tumor tissue sections and corresponding pathological reports or unstained tumor tissue sections (or tissue block) must be collected at screening for central pathology review. Both fresh and archival biopsies are accepted and can be used by central pathology. Investigators may enroll subjects before obtaining the result of central pathology review	
	Efficacy Evaluation	
Radiology	• Baseline radiology assessment methods include contrast- enhanced CT [for head and neck region (that must include nasal cavity, palatum durum, anterior cranial fossa and nasopharynx), chest, abdomen, and pelvis; for patients allergic to CT contrast media, enhanced MRI will be used as an alternative] and systemic PET/CT	
	• Tumor assessment performed with the same machine and method in the same hospital within 28 days before the first dose can be used as the baseline tumor evaluation	
Bone marrow aspiration and biopsy	Bone marrow aspiration and biopsy should be performed. Immunohistochemistry (IHC) analyses should be performed under a microscope no matter bone marrow involves or not (Suggest detecting CD56、TIA-1、CD3、GrB、perforin, and EBER hybridization in situ, etc.)	
Sample Collection for Biomarkers		
Blood samples	Collect 2 mL of whole blood	

Items	Note
Tumor tissue	Seven (7) unstained FFPE tumor tissue slides

6.1.2 Treatment Period

Subjects will receive CS1001 1200 mg IV infusion every 21 days (3 weeks \pm 3 days). All visits will be conducted at the planned time points specified in the protocol.

The items to be completed during the treatment phase are listed in Table 4:

Table 4 Visit	procedures in	n the treatment	phase
----------------------	---------------	-----------------	-------

Items	Note		
Study Management Procedures			
Prior medications and concomitant medications	Concomitant medications are documented		
(Clinical Procedures and Assessments		
Adverse events	Adverse events are recorded		
Height, weight, and vital signs	Vital signs only; within 3 days before dosing in each cycle starting from Cycle 2		
Physical examination and ECOG performance status	Lymphoma-specific physical examination and ECOG performance status evaluation within 3 days before dosing in each cycle starting from Cycle 2		
Labo	oratory Procedures/Assessments (at site)		
Hematology, serum chemistry, urinalysis	Within 3 days before dosing in each cycle starting from Cycle 2		
Thyroid function tests	Within 3 days before dosing every other cycle starting from Cycle 3 (Cycles 3, 5, 7, and so on)		
EBV DNA	Blood sample for EBV DNA test will be collected at each cycle starting from Cycle 2 and every other cycle after radiological CR		
Laboratory 2	Procedures/Assessments (by central laboratory)		
РК	• Blood samples will be collected within 60 minutes before dosing as pre-treatment samples at Cycles 1, 2, 3, 4, and 8, and within 30 minutes after completion of infusion at Cycles 1 and 4		
ADA	• Pre-treatment blood samples are collected (within 60 minutes before dosing) at Cycle 1, 2, 3, 4 and every 4 cycles thereafter (e.g., Cycle 8, 12, 16, and so on)		
Efficacy Evaluation			
Radiology	 Contrast-enhanced CT will be performed every 12 weeks after the first dose of investigational product. Examined sites include head 47/104 		

Confidential

Items	Note
	and neck region (that must include nasal cavity, palatum durum, anterior cranial fossa, and nasopharynx), chest, abdomen, and pelvis. For patients allergic to CT contrast media, enhanced MRI will be used as an alternative.
	 Systemic PET/CT examination will be performed at Week 12 and Week 24. Only enhanced CT will be used for follow-up after first radiological CR or Week 24, whichever comes first. For patients without any measurable lesion, follow-up with PET/CT will be performed until radiological confirmation of CR or progression if the patient hasn't reached CR in the first 24 weeks.
	• Additional PET/CT will be performed if follow-up enhanced CT reveals residual lesion or suspected progression.
Bone marrow aspiration and biopsy	If bone marrow aspiration/biopsy was/were positive or overall bone marrow assessment was indeterminate at screening, bone marrow aspiration and biopsy should be performed when CR is achieved according to radiology. Immunohistochemistry (IHC) analyses should be performed under a microscope no matter bone marrow involves or not (Suggest detecting CD56 TIA-1 CD3 GrB perforin, and EBER hybridization in situ, etc.)

